Mid-Intervention

-Anthropometry, Weight, Treadmill fitness test

Follow-up

	Weight, blood pressure, anthropometry								
	-DEXA, Exercise test, mitochondri	ondrial							
ł	measurements, muscle biopsy								
	-Lipids, insulin, CRP, IVGTT	Figure 3.							
	-FFQ and QOL questionnaire	Study Flow							

Screening visit 1 (SV1): At SV1, fasting blood draws will be performed to evaluate hepatic, renal, hematological, endocrine, lipids, blood chemistries, and metabolic function for inclusion/exclusion purposes. Pre-menopausal women will take a pregnancy test.

Assessment visits: We will obtain primary (CRF) and secondary outcome measures (IVGTT, DEXA, QOL, mitochondrial measures) at baseline and follow-up (24 weeks) (Figure 3). At mid-intervention (week 12), CRF, body weight and anthropometry will be evaluated. At follow-up (week 24), we will re-evaluate all outcomes measures. Randomization (stratified by sex) will occur at the completion of baseline assessments. Additionally, a blood sample (~10 mL) will be obtained at baseline and follow-up and archived at -80°C for future analysis. Exercise intervention: All exercise sessions will be supervised by study staff at the FITT Center (open: 12.5 hrs. Mon-Fri [2.5 hrs.: Sat.], and Heart Institute exercise facilities (open: 6 hrs. Mon-Thurs [4 hrs. Fri.]). All exercise will be performed on a treadmill to maintain close control over kcal expenditure. Participants in the MOD-INT group will exercise at the heart rate associated with 45-55% VO₂ max, and participants in the HIGH-INT group will exercise at a heart rate associated with 70-80% VO₂ max (heart rate ranges will be updated at mid-intervention CRF assessment). The exercise volume for both groups will be 600 MET-minutes per week, which is consistent with current public health guidelines (500-1,000 MET-minutes)³. Since all participants will be sedentary at baseline, we will gradually increase the volume of training. All participants will exercise at 300 MET-minutes during week 1. The volume of exercise will increase 50 MET-minutes per week until they reach the maximum exercise volume of 600 MET-minutes (week 7). Using standard American College of Sports Medicine (ACSM) equations, we will calculate the amount of MET-minutes exercised based on treadmill speed/grade and the participants' weight ⁶¹. Laptop carts with custom-made spreadsheets will be used to track MET-minutes, exercise training data, and aggregation of weekly values (mean RPE, speed, grade, caloric

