
expenditure, etc). Exercise heart rates will be monitored continuously using Zephyr Bioharness 3 monitors (Annapolis, MD to confirm exercise intensity. Adherence to exercise volume will be calculated as MET-minutes exercised divided by required METminutes. Exercise intensity adherence will be quantified as time within the required heart rate range divided by total exercise time.

	· · · · · ·									
	Exercise Intensity	METs	Session time							
))	75% VO₂peak	4.9	~41 min.							
9	50% VO₂ peak	3.3	~61 min.							
	Estimated exercise time (3 times per week) of a woman with VO ₂ peak of 23 ml•kg-1•min-1 at a volume of 600 MET-									
	minutes per week									

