
physical activity, and charge status of all active devices in the study. We will utilize food frequency questionnaires (FFQ) ⁶² to measure estimated daily intake (kilocalories, macronutrients, and micronutrients). 7. Statistical Considerations: Initial CRF will be compared for the three groups using side-by-side boxplots. Side-by-side boxplots will also be made for males and separately for females as we expect the max O2 to be greater for males. Numerical summaries for the boxplots along with mean and standard deviation will be recorded. Outliers and other observations requiring additional scrutiny will be identified. These steps will be repeated for the measurements taken post intervention and for the differences. The groups will be compared in terms age and other covariates using graphs (boxplots for numeric variables and segmented bar plots for categorical data) and numeric summaries. Assuming the descriptive analyses reveal no serious violations of the assumptions, ANOVA will be used to analyze the differences in CRF. In addition to using contrasts for group comparisons, confidence intervals for the difference in means will be reported. Both one-way (factor Group) and two-way (Group and Sex) ANOVA will be used. The analyses described for CRF would also be applied to insulin sensitivity, and other secondary outcomes. Data will be analyzed on an intention to treat basis. We expect attrition rate to be approximately 10-15%. Using -.112, .124, and .200 L/min as the means for the three groups based on previous data ³⁵, a common standard deviation of .250 L/min, and significance level .05, the power ranges from .85 for 15 participants per group to .96 for 20 participants per group. 8. Experience of PI: The PI has 33 publications on exercise training and T2D/CVD risk factors, and is a former NIDDK T-32 postdoctoral fellow (Pennington Biomedical, Mentor: [name].). He has worked on a completed trial on exercise intensity and visceral fat ⁶³. His publications include 3 papers on exercise intensity ^{35,64,65}, 5 papers on racial health disparities ^{9,21,66-68}, and 4 papers dealing with cardiorespiratory fitness as a risk factor for disease ^{21,65,69} (3 specifically on CRF in adults with T2D ⁷⁰⁻⁷²), and a recently published review paper on racial disparities in T2D²⁶. He has been awarded an NIH loan repayment award from NIMHD, and was recently accepted to the NHLBI sponsored PRIDE summer research program for health disparities research. 9. Potential Pitfalls: Recruitment of the necessary sample of African Americans is a potential concern. However, the CHD has documented success with recruitment of African Americans. The PI and the CHD will closely monitor recruitment trends. If the recruitment of participants is below the expected rate, we will develop new recruitment plan to meet the necessary study sample. As the PI is a second year faculty member, another potential pitfall is that the study team has not worked extensively together on a clinical trial. As noted in the study flow diagram (below), during start-up, extensive study planning will take place inclusive of a manual of procedures (MOP), standard operating procedures (SOP), and simulations of data collection of all study visits/databases prior to the start of recruitment. Additionally, Drs. [name] and [name] are co-investigators on the PI's ongoing AHA funded exercise trial at ECU, which currently has 92% exercise adherence (6 month exercise intervention), which suggests the PI is capable of implementing an exercise intervention at his new institution. While the PI will assume complete responsibility of leading this trial, [name] (expertise: large exercise trials/insulin sensitivity, muscle biopsies) will serve as faculty mentor, and the research team will engage in regular study meetings to closely monitor the progress of important indicators of study success (e.g. recruitment rates, adherence to exercise levels and intensity, etc.). If the results of HI-PACE are not supportive of what we have hypothesized on CRF, the secondary measures (insulin sensitivity, skeletal muscle measures, body composition) and archived blood/muscle samples are potential sources to support an R01 application. 10. Conclusion: The HI-PACE study has high public health relevance due to the increased disease burden of T2D and the lack of exercise training studies in African Americans. HI-PACE will be the first study to compare two exercise training programs on T2D risk factors in obese African Americans, and has the potential to influence future physical activity recommendations. We will also obtain valuable psychological parameters of quality of life and enjoyment of exercise, which will help determine whether high intensity aerobic exercise is a feasible strategy over a six month period to improve health outcomes in African Americans. In accordance with the goals of this funding mechanism, the specific direction of the R01 will be dependent on the results of the

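### The CRF change-score ANOVA leaves out baseline CRF; adding it is a cheap, modest gain in precision, not the correction of an error

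*Combined protocol and SAP*

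**What the plan says.** Section 7 (Statistical Considerations) sets the primary analysis: "ANOVA will be used to analyze the differences in CRF". The model terms follow: "Both one-way (factor Group) and two-way (Group and Sex) ANOVA will be used". Neither model contains baseline CRF, which enters Section 7 only descriptively: "Initial CRF will be compared for the three groups using side-by-side boxplots". Age and other covariates are treated the same way: "The groups will be compared in terms age and other covariates using graphs".

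The approach carries over to the remaining endpoints: "The analyses described for CRF would also be applied to insulin sensitivity, and other secondary outcomes".

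The section on assessment visits fixes the order of events: "Randomization (stratified by sex) will occur at the completion of baseline assessments". Baseline CRF is therefore a pre-randomisation measurement that the trial already collects. On losses, Section 7 says: "We expect attrition rate to be approximately 10-15"%.

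**The concern.** Analysing the change score is the same as regressing follow-up CRF on group with the baseline coefficient fixed at 1. The true within-group slope is r × SD2/SD1, where r is the correlation between baseline and follow-up, and SD1 and SD2 are the SDs at those two times. Unless that product is 1, part of any chance baseline difference between arms passes into the group contrast. Randomisation makes this average to zero, so there is no bias, but it adds variance that a measured covariate could remove. Stratifying by sex and putting Sex in the two-way ANOVA deals with the sex-related part of baseline spread. Imbalance within sex remains.

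The stake is precision. Arms are small: 20 each, or 17 after 15% attrition. The trial is also meant to supply estimates for powering a later R01, so narrower intervals are useful and need no new data.

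**Working it through.** **Inputs from Section 7.** Means of -.112, .124 and .200 L/min; common SD .250 L/min; significance level .05; 20 per arm; attrition 10 to 15%, which is 2 to 3 of 20 and leaves 17 or 18.

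**Assumptions.** The means are unlabelled and are read as CON, MOD-INT and HIGH-INT, so HIGH-INT minus MOD-INT is .200 − .124 = .076 L/min. The .250 is read as the SD of change. The documents give neither r nor a baseline SD; r = .7, .8 and .9 with SD1 = SD2 is assumed.

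**1. The plan's own power.** The mean of the three values is .0707 and the sum of squared deviations is .05294. The omnibus F noncentrality at 20 per arm is 20 × .05294/.0625 = 16.94, with 2 and 57 df. Power is .957, matching the stated .96. At 15 per arm the result is .878, against the stated .85. That mismatch is on the conservative side and does not affect this point.

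**2. Variance ratio, ANCOVA to change score.** With equal SDs the large-sample ratio is (1 − r²)/[2(1 − r)] = (1 + r)/2. Estimating the slope multiplies this by 1 + 1/(df − 2): 56/55 = 1.018 at 20 per arm (df = 57) and 47/46 = 1.022 at 17 per arm (df = 48).

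| r | Ratio, 20 per arm | Saving | Ratio, 17 per arm | Saving |
|---|---|---|---|---|
| .7 | .850 × 56/55 = .8655 | 13.5% | .8685 | 13.2% |
| .8 | .900 × 56/55 = .9164 | 8.4% | .9196 | 8.0% |
| .9 | .950 × 56/55 = .9673 | 3.3% | .9707 | 2.9% |
| .95 | .975 × 56/55 = .9927 | 0.7% | .9962 | 0.4% |

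The saving reaches zero at r = 2 × 55/56 − 1 = .964 (20 per arm) or 2 × 46/47 − 1 = .957 (17 per arm). If the true slope is exactly 1, ANCOVA costs 1.8% or 2.2%. Simulation of three arms with change SD .250 gave .866, .917 and .971 at 20 per arm for r = .7, .8 and .9, in line with the formula. In simulation both analyses recover the .076 difference without bias.

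**3. With Sex in both models.** Simulating Group + Sex + baseline against the planned Group and Sex ANOVA, with r now the within-sex correlation, gave ratios of about .867, .916 and .965. The gain survives once sex is modelled.

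**4. What the saving buys at 20 per arm.** The change-score standard error of a pairwise contrast is .250 × √(2/20) = .079 L/min.

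| | Change score | r = .9 | r = .8 | r = .7 |
|---|---|---|---|---|
| 95% CI half-width, L/min | .158 | .156 | .152 | .147 |
| Power, HIGH-INT vs MOD-INT | .157 | .161 | .167 | .174 |
| Equivalent extra participants per arm (20/ratio − 20) | – | 0.7 | 1.8 | 3.1 |

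At 17 per arm power goes from .140 to .143, .148 and .154.

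**5. The same loss seen as a shift.** A one-standard-error baseline gap moves the change-score contrast by (1 − r) × SD1 × √(2/20) = .018, .025 or .031 L/min at r = .9, .8 or .7. This is already inside the .079 standard error and is not a second harm.

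**6. Is the r range reasonable?** With change SD .250, r = 1 − .250²/(2 × SD1²). So r = .7, .8 and .9 imply SD1 = .323, .395 and .559 L/min, and break-even at .964 implies .935. The session-time table under the exercise intervention uses a woman with a peak of 23 ml/kg/min. At BMI 30 to 45 and an assumed height of 1.63 m (80 to 120 kg), that is 1.84 to 2.76 L/min. SDs of .323 to .559 are 12 to 30% of that level; .935 would be 34 to 51%. This makes the assumed range plausible and break-even unlikely. It is not a document figure.

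**The case against.** The strongest case against is that nothing here is a defect. The primary outcome is defined as the change in CRF, and a change-score ANOVA estimates it without bias. On the scales readers use, the gain is slight: intervals narrow by 2 to 7%, and omnibus power at 20 per arm is already .957. All of that stands, and it is why this is a recommendation and not a correction.

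The second argument is that the 3 to 14% range depends on equal SDs. With k = SD2/SD1 the ratio is k²(1 − r²)/(1 + k² − 2rk), times 56/55. If follow-up SD is 10% larger (k = 1.1), the saving is 6.2% at r = .7 and 1.4% at r = .8, and there is a 1.8% loss at r = .9. If it is 10% smaller (k = .9), the saving is about 24%, 20% and 18%. So the sign is not guaranteed inside the assumed r range. This also stands, but the loss cannot go much beyond the roughly 2% price of one estimated slope, while the possible gain is several times larger.

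Two further objections have less force. The formula in step 2 compares models without Sex, but step 3 covers the recommended model and gives nearly the same ratios. For insulin sensitivity and the other secondary outcomes no correlation is known, so no size can be claimed. The same formula says that a less stable outcome gains more: at an assumed r = .5 the saving at 20 per arm would be 1 − .75 × 56/55 = 24%.

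**Conclusion.** The point holds as one of efficiency. Section 7 omits a pre-randomisation covariate that is already collected, and its analysis is valid without it. With equal SDs and r between .7 and .9, adjusting for baseline CRF would save 3.3 to 13.5% of contrast variance at 20 per arm and 2.9 to 13.2% at 17. At 20 per arm that is worth 0.7 to 3.1 participants per arm, against the 2 to 3 the plan expects to lose. Beyond those assumptions the effect runs from a loss of about 2% to a larger saving. The omission itself is certain; its size rests on quantities the documents do not give. HIGH-INT versus MOD-INT power stays near .16 to .17 either way, and no trial conclusion is likely to turn on this choice.

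**What to change.** In Section 7, prespecify as primary an ANCOVA of week-24 CRF (or its change) on group, with baseline CRF and sex as covariates, and report adjusted group contrasts with 95% confidence intervals. Keep the planned change-score ANOVA as a sensitivity analysis. Use the same form for insulin sensitivity and every secondary outcome that has a baseline value. This also names one primary model where the plan now lists two, and settles in advance whether a baseline imbalance seen in the boxplots leads to adjustment.

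The cost is one sentence, one degree of freedom and no new data, with about 2% more variance if the true slope is 1.

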(indirect calorimetry) to adjust the rate predicted from ACSM equations. This has never been performed in an exercise intensity study, and will allows us to more accurately match exercise volume in both groups Skeletal muscle measures will be evaluated to support conclusions on whole body CRF and insulin action **HI-PACE** will be the first study to compare the health benefits of moderate and high intensity exercise training on T2D risk factors specifically in African Americans. The present research will have high public health implications given the substantially greater T2D risk in African Americans compared to Caucasians, and the under-representation of African Americans in physical activity research. The results of HI-PACE will allow us to adequately power our main primary and secondary outcomes to inform the design of an R01 application on exercise intensity in African American adults with a larger array of secondary outcomes. Completion of HI-PACE and the subsequent R01 will likely impact future physical activity recommendations, and will help guide health professionals on the type of exercise to recommend to obese African Americans with high T2D risk. **3.** Approach: The HI-PACE study will enroll 60 sedentary obese African Americans (BMI: 30-45 kg/m², age 40-65 vrs). We will randomize participants to moderate intensity (MOD-INT, n=20), high intensity (HIGH-INT, n=20), or a control group (CON, n=20) for 24 weeks. The primary outcome measure will be the change in CRF following the intervention. Main secondary outcomes include insulin sensitivity measured via an intravenous glucose tolerance test (IVGTT), mitochondrial capacity, skeletal muscle measurements, body fat, c-reactive protein, and psychological outcomes (quality of life/exercise enjoyment).

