Inclusion/exclusion criteria: We will recruit obese (30-45 kg/m²) African Americans (age: 40-65 yrs.) with one additional T2D risk factor. Selection of these risk factors are based on a position stand from the ADA⁵⁰, which provided definitions for impaired fasting glucose, and additional risk factors which are associated with increased risk for T2D (Triglycerides (TG) \geq 150mg/dL, HDL-C < 50 mg/dL or taking cholesterol lowering medications, Blood pressure: systolic \geq 130 mmHG or diastolic \geq 85 mmHg or the use of BP medication, Fasting glucose 100-125 mg/dL, waist circumference \geq 88cm). All participants must be sedentary/low active (step count \leq 6,500 step/day) and not participating in exercise training (\geq 20 minutes on \geq 3 days per week for the last 3 months). We will exclude participants with diagnosed T2D (or blood glucose value>125 mg/dL) or known cardiovascular diseases, excessively high resting blood pressure (systolic >180 mmHg and diastolic >100 mmHg), significant medical conditions, life threatening conditions, pregnancy or plans to become pregnant, conditions that are contraindicated for exercise. In addition, we will exclude individuals who have plans to diet or engage in weight loss, or demonstrate non-compliance during screening visits. Primary Outcome- CRF: We have selected CRF as the primary outcome measurement due to the wellestablished association between CRF levels and T2D⁴⁻⁷. We will measure CRF by maximal oxygen consumption from a maximal exertion treadmill test, which is considered the gold standard technique. Maximal Exercise Test: We will use a modified Balke treadmill (Trackmaster 425, Carefusion, Newton Kansas) protocol to determine CRF, and the appropriate heart rate range for aerobic exercise training. Participants will walk at an initial speed of 2.0 mph with 0% grade for the first 2 minutes after which the treadmill speed will increase to 3.0 mph for the next 2 minutes. Treadmill grade will be increased by 2.5% every 2 minutes until volitional exhaustion. Respiratory gases (VO₂, CO₂) and ventilation will be measured continuously using a True Max 2400 Metabolic Measurement Cart (Parvomedics, Salt Lake City, Utah). **Secondary outcomes**: The majority of secondary measures will be evaluated at baseline and follow-up. Exceptions to this are anthropometry, CRF, and weight data which will also be evaluated at mid-intervention (see Figure 3), and exercise enjoyment/affective valence measures which will occur during exercise sessions. **IVGTT:** Insulin sensitivity will be assessed at baseline and follow-up (24 hours following the last exercise session in exercise groups). After the collection of fasting blood samples, glucose (50%) will be injected into a catheter placed in the antecubital vein at a dose of 0.3 g/kg body weight. Subsequently, blood samples will be obtained at the following time points: 2, 3, 4, 5, 6, 8, 10, 12, 14, 16, 19, 22, 25, 30, 40, 50, 60, 70, 80, 90, 100, 120, 140, 160, and 180 min. Insulin will be injected at minute 20 of the test at a dose of 0.025 U/kg body mass. Blood samples will be centrifuged, and stored at -80°C until sample analysis for glucose and insulin. insulin sensitivity index will be determined through a minimal model ⁵¹.

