Other secondary measures: Body weight will be evaluated a calibrated scale, with the participant fasted and wearing only a hospital gown. Dual Energy X-ray Absorptiometry (DEXA) will be used to measure body composition (fat and lean mass). C-reactive protein (CRP) will be measured using standard analytical techniques. Waist circumference will be evaluated with a gulick tape measure, and recorded at the natural waist. Quality of life (QOL) will be measured by the short form health survey (SF-36)⁵⁷. Exercise enjoyment will be assessed via a 5-item short version of the commonly used Physical Activity Enjoyment Scale (PACE)^{58,59} and will be during exercise training sessions. Affective valance (pleasure/displeasure) will be assessed during exercise training from -5 (very bad) to +5 (very good) with 0 representing neutral feelings. **4. Recruitment:** Participants will be recruited primarily through the ECU Center of Health Disparities (CHD) (directed by [name]., letter of support included). The Community Core of the CHD specializes in recruiting African Americans for research and clinical trials. The Core produces expertly-designed, culturally-tailored recruitment flyers, DVDs, CDs etc., and distributes these through community partners. Using these strategies, the Core has recruited more than **400 African American adults** per year for research. For the present proposal, the Core will design recruitment flyers tailored for African Americans; distribute these in six

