local community settings frequented by them; distribute these to their partners; advertise the project on the Center's African-American community website, Minority Health Matters; and maintain a phone number to answer potential-participants' questions. We will also utilize standard techniques (advertisement, ECU email server, flyering). 5. Pre-screening: After phone-screen, individuals will be invited to an orientation session, where we will provide information about the study design, procedures, and risks/benefits. Individuals interested in participation will be consented, and scheduled for run-in visits. Run-in visits: The purpose of the run-in visit is to ensure participants are able to make the time commitment to come to ECU approximately three times per week. In our past training studies, this run-in period has helped to obtain excellent training adherence by allowing potential participants to fully evaluate their ability to commit to study time demands. To simulate participation in HI-PACE, run-ins sessions will be scheduled 3 sessions per week over the course of one week, and duration will be similar to training sessions (~30-60 minutes). Study staff will verify sedentary status, and screen for other inclusion/exclusion criteria (e.g. medical history questionnaire/study surveys, BMI, waist circumference, blood pressure assessment, etc.). As a safeguard against low exercise adherence, participants will complete an exercise calendar (identification of expected exercise days/times, and potential back-up times). Participants will also complete a questionnaire on time commitments, child/elder care, distance from the exercise facility, motivations for exercise, family support.

Phone Screening : Age (40-65 yrs.), BMI (30-45), Diabetes (NO), Heart disease (NO), sedentary, African American (YES), Contact info

Orientation

-Informational session about study requirements -Obtain consent for screening and run-in visits

Run-in visits

-3 run sessions over 1 weeks to test participants ability to come to ECU 3 times per week - Verify inclusion criteria (ie: baseline physical activity, waist circumference, blood pressure). -Collection of FFQ and QOL questionnaires

SV1

- Obtain consent for main study - Physical exam/review of medications -Lipids, CBC, Chem panel, insulin

Baseline

- Weight, blood pressure, anthropometry, CRP, DEXA, Exercise test, mitochondrial measurements, muscle biopsy, IVGTT, FFQ, QOL -Randomization (CON, LOW-INT, HIGH-INT)

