Exercise economy: To address potential variability in economy during training at a given exercise workload, we will also directly measure energy expenditure (EE) rate by indirect calorimetry at the prescribed exercise intensity at baseline, every two weeks during the first month of the study, and then monthly until the conclusion of the intervention. The rate of EE determined by indirect calorimetry will be divided by the EE estimated by ACSM equations (actual EE rate/predicted EE rate) to develop a correction factor. This correction factor will be used to adjust the EE calculated from ACSM equations within our exercise training spreadsheet to more accurately implement the EE which corresponds with 600 MET-minutes per week at both intensities. Psych. exercise session data: During exercise training sessions, affective valence (Feeling scale) will be assessed at exercise sessions at rest, every 10 minutes during exercise, and at 5 minutes post-exercise. The PACE scale (exercise enjoyment) will be measured at 5 minutes after the completion of the exercise session. Promotion of high exercise adherence: The HI-PACE study has several protocols to promote high exercise adherence during the intervention: 1) Participants will complete an exercise calendar during screening (described above), and the first exercise session of the each week during intervention (e.g. planned exercise days, planned back-up days). 2) Bi-weekly progress reports (e.g. adherence rate, miles walked, heart rate compliance) will be provided to participants to increase intrinsic motivation for attainment of exercise goals. 3) We will actively monitor exercise adherence on a weekly basis in study meetings. Participants with adherence levels <75% or display major warning signs for low adherence (e.g. frequent rescheduling, missed sessions, low morale) will be assigned a "case manager" from the staff to create a plan to intervene and improve exercise levels and problem solve the causes of poor adherence. 4) Participants missing an exercise session will be contacted by the exercise intervention coordinator immediately and rescheduled for a make-up session. 6. Dietary assessment and non-exercise physical activity: Participants in all groups will be asked not to alter dietary habits or non-exercise physical activity during the study. Non-exercise physical activity will be tracked using the Fitbit Flex (Fitbit Inc., San Francisco, CA) in all randomization groups. The Fitbit Flex will be worn in blind-mode (steps will not be represented on the device display), and the device will be removed during exercise training sessions for participants in the exercise training groups. Control participants will upload their data using Fitbit software at home. Staff will use a database program (Fitabase[®], Small Steps Labs) to centralize all non-exercise physical activity data from the Fitbits inclusive of steps, moderate to vigorous

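### Does the three-group change-score ANOVA leave exercise enjoyment and affective valence without a workable analysis?

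*Combined protocol and SAP*

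**What the plan says.** Section 7 (Statistical Considerations) describes the fitness analysis: summaries at baseline, after the intervention and for the differences, then ANOVA of the differences by group, and by group and sex, with contrasts and confidence intervals for differences in means. It then says: "The analyses described for CRF would also be applied to insulin sensitivity, and other secondary outcomes". No other rule is given for secondary outcomes.

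Section 3 (Approach) closes its list of main secondary outcomes with "psychological outcomes (quality of life/exercise enjoyment)". Affective valence appears only later, under Other secondary measures.

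The timing of both scales is set apart. The Secondary outcomes paragraph lists, as an exception to the baseline and follow-up schedule, "exercise enjoyment/affective valence measures which will occur during exercise sessions". Other secondary measures says of the enjoyment scale, "and will be during exercise training sessions". The paragraph on psychological session data adds: "The PACE scale (exercise enjoyment) will be measured at 5 minutes after the completion of the exercise session". Valence is rated there at rest, every 10 minutes during exercise, and 5 minutes afterwards.

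In Figure 3 the baseline battery includes "DEXA, Exercise test, mitochondrial measurements, muscle biopsy, IVGTT, FFQ, QOL" and the follow-up list ends with "FFQ and QOL questionnaire". Neither names the enjoyment or valence scale.

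**The concern.** Taken literally, the Section 7 rule needs a baseline value, a week-24 value and three groups. The two session-based scales have no baseline value, because randomisation follows the baseline assessments and every training session comes after it. They also appear to have no third group, since training is described only for MOD-INT and HIGH-INT.

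The plan does not say that these scales are compared between two arms, which sessions count, or how many ratings become one value per participant. Section 10 (Conclusion) says that quality of life and enjoyment will help show whether high-intensity exercise is feasible over six months. The stated analysis suits quality of life but not enjoyment. An unwritten choice of summary could, in principle, be made with the results in view.

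**Working it through.** **1. Rule against data.**

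| Requirement of the Section 7 rule | Quality of life | Enjoyment | Affective valence |
|---|---|---|---|
| Value before randomisation | Yes (Figure 3, baseline) | No | No |
| Value at the week-24 assessment | Yes (Figure 3, follow-up) | No, sessions only | No, sessions only |
| Values in the control group | Yes | None, by inference | None, by inference |

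The valence rating at rest allows a within-session change, which is not a change over the trial. The control-group entries are inferred. The sentence "All participants will exercise at 300 MET-minutes during week 1" might seem to include controls, but it stands in the Exercise intervention paragraph after the volume has been set for the two training groups. Section 6 likewise ties training sessions to the exercise groups.

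**2. Participants available.** Two arms of 20 give 20 + 20 = 40 of 60. The 10-15% attrition in Section 7 cannot simply be subtracted. A participant who leaves partway has already given session ratings and still has a summary, so the supportable figure is up to 40.

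**3. Precision.** With 20 per arm and a two-sided 5% t test, a comparison of one summary per participant has 80% power for a difference of about 0.91 SD. The normal approximation is close: (1.96 + 0.84) × √(2/20) = 0.89 SD. Writing the two-arm comparison into the plan would not alter this.

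**4. Session length.** The plan's example woman has a VO2peak of 23 ml/kg/min.

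- Capacity: 23 / 3.5 = 6.57 METs.
- 75%: 0.75 × 6.57 = 4.93 METs. 50%: 0.50 × 6.57 = 3.29 METs. The plan prints 4.9 and 3.3.
- Full volume: 600 / 3 = 200 MET-minutes per session.
- HIGH-INT: 200 / 4.93 = 40.6 min. MOD-INT: 200 / 3.29 = 60.8 min. The plan prints about 41 and 61, so its table reproduces.
- Week 1: 300 / 3 = 100 MET-minutes, giving 100 / 4.93 = 20.3 min and 100 / 3.29 = 30.4 min.

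**5. What this means for each scale.**

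- *Valence:* ratings every 10 minutes give about 4 against 6 in-exercise values at full volume, and about 2 against 3 in week 1. A mean, a last rating and a rating at a fixed minute fall at different points of the session in the two arms.
- *Enjoyment:* one rating after the session in either arm. Over at most 3 × 24 = 72 sessions, the natural summary is the participant's mean, and session length does not change the number of ratings per session.

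**The case for a change.** The strongest case for a change is that an unspecified summary is an avoidable freedom in the analysis. Enjoyment is named as a main secondary outcome, Section 10 relies on it, and two or three sentences would settle the matter at almost no cost and without new data. For valence the choice of summary could affect the comparison, because sessions of equal volume last 75/50 = 1.5 times as long in MOD-INT at the nominal intensities.

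Much of this stands. The rule cannot be applied literally, and the valence summary is open. Three parts are weaker:

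- The documents do not show that the choice would be made after the data are seen, only that it is not recorded here.
- The session-length argument concerns valence, which is neither on Section 3's main list nor mentioned in Section 10. It does not reach enjoyment, the outcome on which the feasibility argument rests.
- The measurement sections openly exempt both scales from the baseline and follow-up schedule, so a reader is not led to expect change scores for them.

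**Conclusion.** No change follows; this is a gap that an analyst fills sensibly. The inapplicable rule produces no wrong number, because a three-group change-score ANOVA cannot be run on data that do not exist. The tools in Section 7, group contrasts and confidence intervals for a difference in means, carry over directly to the two arms that have ratings, using one value per participant.

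The extent is limited to two session-based psychological scales and up to 40 participants. Both specific aims concern fitness and insulin sensitivity. The fallback measures that Section 9 names for a later grant application are insulin sensitivity, skeletal muscle measures and body composition. Section 10 gives enjoyment a supporting role, with no threshold or decision attached. The power statement concerns fitness alone.

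The conclusion assumes that controls attend no training sessions, which is the natural reading although the control condition is not described in detail. It also assumes that the participant, rather than the session, is the unit of inference. A valence result should be read with its chosen summary in mind, but that is a point of interpretation for a minor outcome.
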